Eligibility Criteria

- Histologically confirmed melanoma that is recurrent/metastatic and not amenable to potentially curative surgery;
- Clinically and/or radiologically documented disease with at least one site of disease unidimensionally measurable by contrast-enhanced CT scan;
- Radiology must be performed within 28 days prior to registration (35 days if negative);
- Age \geq 18 years;
- ECOG 0 to 1;
- Previous surgery permitted as long as 21 days prior to patient registration and wound healing has occurred;
- Palliative radiation permitted as long as >7 days between last dose and enrolment on trial;
- Neutrophils $\geq 1.5 \times 10^9/L$;
- Platelets $\geq 100 \times 10^9/L$;
- Hemoglobin $\geq 90 \text{ g/L}$ or $\geq 5.6 \text{ mmol/L}$ (without transfusion or EPO dependency);
- Serum creatinine $\leq 1.5 \times \text{ULN}$ **OR** measured or calculated creatinine clearance $\geq 60 \text{ mL/min}$ for subject with creatinine levels $> 1.5 \times \text{ULN}$;
- Serum total bilirubin $\leq 1.5 \times \text{ULN}$ **OR** direct bilirubin $\leq \text{ULN}$ for subjects with total bilirubin levels $> 1.5 \times \text{ULN}$;
- AST and ALT $\leq 2.5 \times \text{ULN}$ ($\leq 5 \times \text{ULN}$ for subjects with liver mets);
- Albumin $\geq 25 \text{ g/L}$;
- Negative serum or urine pregnancy test within 7 days prior to registration (if applicable);
- Men and women of child-bearing potential must use adequate contraception as described in Section 5.1.7.

Ineligibility Criteria

- Prior systemic therapy for metastatic melanoma;
- Known history of Human Immunodeficiency Virus (HIV) (HIV 1/2 antibodies);
- Known history of or known positive for Hepatitis B (HBsAg reactive) or Hepatitis C (HCV RNA [qualitative] is detected). Patients with unknown history of HBV or HCV will require screening;
- Patients with previously treated brain metastases may participate provided they are stable with no evidence of enlargement following radiation treatment and no acute radiation toxicity **OR** no evidence of enlargement at least 4 weeks prior to the first dose of study drug if untreated and are off systemic steroids for at least two weeks;
- Patients who are pregnant or breastfeeding, or expecting to conceive or father children within the projected duration of the study;

AMEND #1: 2016-NOV-23; AMEND #2: 2017-JUL-10

- Patients who previously had a severe hypersensitivity reaction to treatment with another mAb;
- Patients with an active autoimmune disease or a documented history of autoimmune disease or syndrome that requires systemic steroids or immunosuppressive agents;
- Patients with a history of a malignancy (other than the disease under treatment in the study) within 5 years prior to first study drug administration;
- Patients on any systemic corticosteroid therapy within one week before the planned date for first dose of treatment or on any other form of immunosuppressive medication;
- Patients with an allergy to iodinated contrast media used for CT;
- Patients with a known history of active TB (Bacillus Tuberculosis);
- Patients with evidence of interstitial lung disease;
- Patients with known history of, or any evidence of active, non-infectious pneumonitis.

Pre-Treatment Evaluations

- History, physical exam, ECOG performance status, vital signs, toxicity/baseline symptoms (within 14 days prior to registration);
- Hematology and biochemistry (within 7 days prior to registration);
- Pregnancy test (within 7 days prior to registration, if applicable);
- ECG (within 7 days prior to registration if not done within 6 months);
- Health Utilities Index (EQ-5D) (within 7 days prior to registration);
- CT scan with contrast of chest, abdomen/pelvis (within 28 days prior to registration; 35 days if negative).

Treatment

- Pembrolizumab will be given intravenously day 1 every 3 weeks

On-Treatment Evaluations

- History and physical exam, ECOG (Day 1 each cycle)
- Vital signs (blood pressure and pulse) (Day 1 each cycle)
- Hematology and Biochemistry (Day 1 each cycle)
- TSH, FT3, FT4 (every other cycle)
- CT scan with contrast of chest, abdomen/pelvis (4 weeks, 12 weeks, then every 12 weeks)
- ECG (as clinically indicated)
- Health Utilities Index (EQ-5D) and Resource Utilization Assessment (each 12 weekly visit until progression OR maximum 1 year from registration)
- Adverse events – patients to be evaluated continuously for adverse events.

Duration of Treatment

See Section 12.

AMEND #1: 2016-NOV-23

1.0 OBJECTIVES

1.1 Primary Objective

To assess whether tumour texture parameters from a CT scan can differentiate patients who do and who do not respond to treatment with pembrolizumab.

1.2 Secondary Objectives

- To assess whether tumour texture parameters from a CT scan can correlate with time to disease progression in patients with metastatic melanoma being treated with pembrolizumab.
- To assess duration of response (DoR).
- To assess overall response rate (ORR, PR, CR).
- To assess overall survival (OS).
- To compare cost per quality adjusted life years (QALY) between pembrolizumab and dacarbazine.
- To compare cost per quality adjusted life years (QALY) between pembrolizumab and ipilimumab.
- Toxicity using the CTCAE v.4.

2.0 BACKGROUND INFORMATION AND RATIONALE

Metastatic melanoma historically has had a very poor survival. Thankfully this is now changing due to advent of new targeted drugs and breakthroughs in immunotherapy. Programmed cell death 1 (PD-1) receptor is an inhibitory receptor expressed by T cells. Its ligand, PD-L1 is frequently expressed within the tumour microenvironment including tumour cells. Tumour models have shown that PD-1 negatively regulates the effector phase of T-cell responses after ligation of PD-L1 expressed within the tumour [Blank 2004]. Several drugs have been developed that block PD-1 and hence augment the T cell response. The most mature results have been obtained in advanced melanoma patients and indicate high response rates, high quality responses and prolonged duration of response and prolonged survival.

Pembrolizumab is a highly selective, humanized monoclonal IgG4-kappa isotype antibody against PD-1 that is designed to block the negative immune regulatory signalling of the PD-1 receptor expressed by T cells [Hamid 2013]. Pembrolizumab has shown improved response rates, response duration and survival compared to standard treatments for melanoma [Ribas 2015; Patnaik 2014]. Patients receiving pembrolizumab had an overall RR of 38% with durable responses and approximately a further 30% of patients with disease control. The 1 year survival in this trial was 67% and 50% at 2 years in patients with metastatic melanoma [Daud 2015]. Pembrolizumab was also compared to ipilimumab in first line therapy for metastatic melanoma and showed a better RR and OS rate compared to ipilimumab with a RR of 34% compared to 12% and OS at 12 months of 74% compared to 58% for ipilimumab [Robert 2015]. In this study and subsequent phase III studies, pembrolizumab is administered intravenously at 2 mg/kg every 2 weeks for a total of 2 years. Recent results from pharmacokinetic studies indicate that a flat dose of 200 mg IV is sufficient for exposure and that there is no additional advantage to weight-based dosing. In addition, responses occur early within the first 8 weeks and it is possible that 2 years of consecutive therapy may not be needed given the durable responses seen with ipilimumab short courses.

Imaging is widely used in oncology for confirmation of diagnosis, staging and assessing treatment response. Tumour heterogeneity, such as heterogeneity of the tumour blood supply is a well-recognized feature of malignancy. Computed tomographic (CT) texture analysis is a form of quantitative feature analysis that focuses on the heterogeneity of attenuation within tumours [Goh 2011]. Evidence suggests that texture analysis has the potential to augment diagnosis by differentiating between benign and malignant neoplasms, tumour staging by differentiating between invasive and non-invasive disease and malignant/non-malignant lymph nodes, and therapy response assessment in oncological practice [De Ruysscher 2013; Bayanati 2014]. Characteristics such as textural heterogeneity on a CT scan have been used to predict response and time to progression in renal cell carcinoma (RCC) and non-small cell lung carcinoma (NSCLC) patients [Goh 2011; Win 2013]. In metastatic renal cell cancer patients on TKIs, texture analysis was shown to be an independent factor associated with time to progression [Goh 2011].

AMEND #1: 2016-NOV-23

Our investigators have previously evaluated and confirmed the prognostic value of texture analysis in RCC. To our knowledge the potential of texture analysis has not been explored in patients with metastatic melanoma. However, its application in patients with advanced melanoma who are candidates for immunotherapy is reasonable and may be quite valuable. We hypothesize that texture analysis will differentiate responders/non-responders to pembrolizumab and differentiate between pseudoprogression from true disease progression. The benefits of imaging biomarker would be several: identification of patients for treatment, early discontinuation for failure of response, and appropriate continuation of treatment in patients with pseudoprogression. By limiting the numbers of patients receiving treatment that are not benefiting, the overall cost effectiveness of treatment and overall benefit to Canadian patients and the Canadian health care system is increased.

We are proposing a phase II study in metastatic melanoma patients treated with pembrolizumab 200 mg IV q 3 weeks to assess whether tumour texture parameters from a CT scan can differentiate time to progression and response. Patients will be followed on study for a maximum of 12 months. The trial will be sponsored and conducted by the Canadian Cancer Trials Group, Canada's largest adult cooperative cancer clinical trials group. The group has conducted more than 400 phase I-III trials in all cancer settings and all modalities of treatment. The Melanoma Disease Site Committee of the CCTG has successfully conducted several early phase clinical trials testing novel treatments in melanoma at cancer centres across the country. The group will collaborate with experienced imaging researchers at Sunnybrook and OICR to ensure quality of acquisition and interpretation of CT images.

The choice of the 200 mg Q3W as an appropriate dose for the switch to fixed dosing is based on simulations performed using the population PK model of pembrolizumab showing that the fixed dose of 200 mg every 3 weeks will provide exposures that 1) are optimally consistent with those obtained with the 2 mg/kg dose every 3 weeks, 2) will maintain individual patient exposures in the exposure range established in melanoma as associated with maximal efficacy response and 3) will maintain individual patients exposure in the exposure range established in melanoma that are well tolerated and safe.

A fixed dose regimen will simplify the dosing regimen to be more convenient for physicians and to reduce potential for dosing errors. A fixed dosing scheme will also reduce complexity in the logistical chain at treatment facilities and reduce wastage.

3.0 BACKGROUND THERAPEUTIC INFORMATION

[REDACTED]

PROTOCOL DATE: 2016-MAR-03
CCTG TRIAL: IND.225

[REDACTED]

[REDACTED]

[REDACTED]

[REDACTED]

[REDACTED]

4.0 TRIAL DESIGN

This is an open-label, multicentre, phase II trial of pembrolizumab in first line therapy of metastatic melanoma. This trial is being conducted by the Canadian Cancer Trials Group with the support of Merck.

AMEND #1: 2016-NOV-23

5.0 STUDY POPULATION

This study is designed to include women and minorities as appropriate, but is not designed to measure differences in intervention effects.

5.1 Eligibility Criteria

There will be NO EXCEPTIONS to eligibility requirements at the time of registration. Questions about eligibility criteria should be addressed prior to registration.

The eligibility criteria for this study have been carefully considered. Eligibility criteria are standards used to ensure that patients who enter this study are medically appropriate candidates for this therapy. For the safety of the patients, as well as to ensure that the results of this study can be useful for making treatment decisions regarding other patients with similar diseases, it is important that no exceptions be made to these criteria for admission to the study.

Patients must fulfill all of the following criteria to be eligible for admission to the study:

- 5.1.1 Histologically confirmed melanoma that is recurrent/metastatic and not amenable to potentially curative surgery.
- 5.1.2 Presence of clinically and/or radiologically documented disease based on RECIST 1.1. At least one site of disease must be unidimensionally measurable by contrast-enhanced CT scan as follows:

CT scan (with slice thickness of ≤ 5 mm)	≥ 10 mm	→ longest diameter
Lymph nodes by CT scan	≥ 15 mm	→ measured in short axis

All radiology studies must be performed within 28 days prior to registration and meet the criteria outlined in Appendix VI (exception: within 35 days if negative).

- 5.1.3 Age ≥ 18 years.
- 5.1.4 ECOG Performance Status of 0 to 1.
- 5.1.5 Previous Therapy

Surgery:

Previous surgery is permitted provided that it has been at least 21 days prior to patient registration and that wound healing has occurred.

Systemic Therapy:

Patients may not have received any prior systemic therapy for metastatic melanoma.

Radiation:

Palliative radiation is permitted provided > 7 days has elapsed between last dose and enrollment on the trial.

Admin Update #1: 2016-MAY-10; AMEND #2: 2017-JUL-10

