10.2.3 Target Lesions. When more than one measurable tumour lesion is present at baseline all lesions up to *a maximum of 5 lesions total* (and a maximum of *2 lesions per organ*) representative of all involved organs should be identified as target lesions and will be recorded and measured at baseline. Target lesions should be selected on the basis of their size (lesions with the longest diameter), be representative of all involved organs, but in addition should be those that lend themselves to *reproducible repeated measurements*. Note that pathological nodes must meet the criterion of a short axis of ≥ 15 mm by CT scan and only the *short axis* of these nodes will contribute to the baseline sum. All other pathological nodes (those with short axis ≥ 10 mm but < 15 mm) should be considered non-target lesions. Nodes that have a short axis < 10 mm are considered non-pathological and should not be recorded or followed (see 10.2.4). At baseline, the sum of the target lesions (longest diameter of tumour lesions plus short axis of lymph nodes: overall maximum of 5) is to be recorded. **Note: For this study, skin lesions will be considered as non-target lesions.**

AMEND #1: 2016-NOV-23

After baseline, a value should be provided on the CRF for all identified target lesions for each assessment, even if very small. If extremely small and faint lesions can not be accurately measured but are deemed to be present, a default value of 5 mm may be used. If lesions are too small to measure and indeed are believed to be absent, a default value of 0 mm may be used.

10.2.4 *Non-target Lesions*. All non-measurable lesions (or sites of disease) plus any measurable lesions over and above those listed as target lesions are considered *non-target lesions*. Measurements are not required but these lesions should be noted at baseline and should be followed as “present” or “absent”. **Note: For this study, skin lesions will be considered as non-target lesions.**

10.2.5 *Response*.

All patients will have their BEST RESPONSE from the start of study treatment until the end of treatment classified as outlined below:

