Complete Response (CR): disappearance of *target* and *non-target* lesions and normalization of tumour markers. Pathological lymph nodes must have short axis measures < 10 mm (*Note*: continue to record the measurement even if < 10mm and considered CR). Residual lesions (other than nodes < 10 mm) thought to be non-malignant should be further investigated (by cytology specialized imaging or other techniques as appropriate for individual cases *[Eisenhauer 2009]* before CR can be accepted. Confirmation of response is only required in non-randomized studies.

Partial Response (PR): at least a 30% decrease in the sum of measures (longest diameter for tumour lesions and short axis measure for nodes) of target lesions, taking as reference the baseline sum of diameters. Non target lesions must be non-PD. Confirmation of response is only required in non-randomized studies.

Stable Disease (SD): Neither sufficient shrinkage to qualify for PR nor sufficient increase to qualify for PD taking as reference the smallest sum of diameters on study.

Progressive Disease (PD): at least a 20% increase in the sum of diameters of measured lesions taking as references the smallest sum of diameters recorded on study (including baseline) AND an absolute increase of $\geq 5\text{mm}$. Appearance of new lesions will also constitute progressive disease (including lesions in previously unassessed areas). In exceptional circumstances, unequivocal progression of non-target disease may be accepted as evidence of disease progression, where the overall tumour burden has increased sufficiently to merit discontinuation of treatment or where the tumour burden appears to have increased by at least 73% in volume. Modest increases in the size of one or more non-target lesions are NOT considered unequivocal progression. If the evidence of PD is equivocal (target or non-target), treatment may continue until the next assessment, but if confirmed, the earlier date must be used.

Patients that are clinically well may continue on therapy following RECIST progression with new lesions or increase in target lesions if the increase in disease burden does not meet the definition of PD by immune response criteria *[Seymour 2016]*. In this situation, patients do not have unequivocal progression until immune response criteria are met (see Table 2 below).

AMEND #1: 2016-NOV-23

Table 1: Integration of Target, non-Target and New Lesions into Response Assessment:

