Target Lesions	Non-Target Lesions	New Lesions	Overall Response	Best Response for this Category also Requires
Target lesions ± non target lesions				
CR	CR	No	CR	Normalization of tumour markers, tumour nodes <10mm
CR	Non-CR/Non-PD	No	PR	
CR	Not all evaluated	No	PR	
PR	Non-PD/ not all evaluated	No	PR	
SD	Non-PD/ not all evaluated	No	SD	documented at least once \geq 4 wks. from baseline
Not all evaluated	Non-PD	No	NE	
PD	Any	Any	PD	
Any	PD	Any	PD	
Any	Any	Yes	PD	
Non target lesions ONLY				
No Target	CR	No	CR	Normalization of tumour markers, tumour nodes < 10mm
No Target	Non-CR/non-PD	No	Non-CR/non-PD	
No Target	Not all evaluated	No	NE	
No Target	Unequivocal PD	Any	PD	
No Target	Any	Yes	PD	
Note: Patients with a global deterioration of health status requiring discontinuation of treatment without objective evidence of disease progression at that time should be reported as "symptomatic deterioration". This is a reason for stopping therapy, but is NOT objective PD. Every effort should be made to document the objective progression even after discontinuation of treatment.				

Immune-Related Response Assessment

Overall response will also be assessed using iRECIST [Seymour 2016]. Immunotherapeutics may result in infiltration of immune cells leading to transient increase in the size in malignant lesions, or undetectable lesions becoming detectable. The criteria are identical to those of RECIST 1.1 in many respects but have been adapted to account for instances where an increase in tumour burden, or the appearance of new lesions, does not reflect true tumour progression.

Key differences are described below. All responses defined using iRECIST criteria are designated with a prefix. iRECIST time-point and best overall responses will be recorded separately.

AMEND #1: 2016-NOV-23

Confirming Progression

Unlike RECIST 1.1, iRECIST requires the confirmation of progression and uses the terms iUPD (unconfirmed progression) and iCPD (confirmed progression). Confirmatory scans should be performed at least 4 weeks, but no longer than 8 weeks after iUPD.

iCPD is confirmed if further increase in tumour burden, compared to the last assessment, is seen as evidenced by one or more of the following:

- Continued increase in tumour burden (from iUPD) where RECIST 1.1 definitions of progression had been met (from nadir) in target, non-target disease or new lesions
 - Progression in target disease worsens with an increase of at least 5 mm in the absolute value of the sum

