- For patients with non-target disease only at baseline, only CR or non-CR/non-PD can be assigned at each TPR but is not shown in the table for ease of presentation.

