10.5 Methods of Measurement

The same method of assessment and the same technique should be used to characterize each identified and reported lesion at baseline and during follow-up. Assessments should be identified on a calendar schedule and should not be affected by delays in therapy. While on study, all lesions recorded at baseline should have their actual measurements recorded at each subsequent evaluation, even when very small (e.g. 2 mm). If it is the opinion of the radiologist that the lesion has likely disappeared, the measurement should be recorded as 0 mm. If the lesion is believed to be present and is faintly seen but too small to measure, a default value of 5 mm should be assigned. For lesions which fragment/split add together the longest diameters of the fragmented portions; for lesions which coalesce, measure the maximal longest diameter for the “merged lesion”.

- 10.5.1 **Clinical Lesions**. Clinical lesions will only be considered measurable when they are superficial and ≥ 10 mm as assessed using calipers (e.g. skin nodules). For the case of skin lesions, documentation by colour photography including a ruler to estimate the size of the lesion is recommended. If feasible, imaging is preferred.
- 10.5.2 **Chest X-ray**. Chest CT is preferred over chest X-ray, particularly when progression is an important endpoint, since CT is more sensitive than X-ray, particularly in identifying new lesions. However, lesions ≥ 20 mm on chest X-ray may be considered measurable if they are clearly defined and surrounded by aerated lung.
- 10.5.3 **CT, MRI**. For this protocol the baseline CT scans within the first 12 weeks must conform to the requirements outlined in Appendix VII. For assessment of response using RECIST 1.1, CT is the best currently available and reproducible method to measure lesions selected for response assessment. This guideline has defined measurability of lesions on CT scan based on the assumption that CT slice thickness is 5 mm or less. Other specialized imaging or other techniques may also be appropriate for individual case [ref RECIST 1.1]. For example, while PET scans are not considered adequate to measure lesions, PET-CT scans may be used providing that the CT conforms to Appendix VII.
- 10.5.4 **Ultrasound**. Ultrasound is not useful in assessment of lesion size and should not be used as a method of measurement. If new lesions are identified by ultrasound in the course of the study, confirmation by CT is advised.

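### Section 5.1.2 admits patients whose only CT-measurable disease is a skin lesion, but 10.2.3 and 10.2.4 make skin lesions non-target, so these patients can count as responders only through CR

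*Combined protocol and SAP*

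**What the plan says.** **Entry.** Section 5.1.2 states: "At least one site of disease must be unidimensionally measurable by contrast-enhanced CT scan as follows", with limits of 10 mm longest diameter, or 15 mm short axis for nodes. The eligibility list in the synopsis also asks for "at least one site of disease unidimensionally measurable by contrast-enhanced CT scan". Neither mentions target lesions or treats skin separately, and I found nothing in 5.2 that does.

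**Lesion class.** Sections 10.2.3 and 10.2.4 carry the same study-specific note: "For this study, skin lesions will be considered as non-target lesions". Section 10.2.1 would otherwise count a lesion of 10 mm or more on CT or clinical examination as measurable. Section 10.5.1 gives skin nodules as its example of measurable clinical lesions and prefers imaging where feasible.

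**Scoring.** Under 10.2.5, PR needs "at least a 30% decrease in the sum of measures (longest diameter for tumour lesions and short axis measure for nodes) of target lesions". Table 1 has a separate block headed "Non target lesions ONLY", whose outcomes are CR, Non-CR/non-PD, NE and PD. A note to Table 3 says the same for iRECIST: "For patients with non-target disease only at baseline, only CR or non-CR/non-PD can be assigned at each TPR".

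**Use.** Section 10.1.2 makes a patient evaluable for response after one cycle and a disease re-evaluation, with no target-lesion condition. Section 1.2 describes ORR in terms of PR and CR. Sections 1.1 and 14.2 compare texture between responders and non-responders.

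**The concern.** The entry rule and the response rule use different definitions of usable disease. The primary objective depends on a two-way label, responder or non-responder. For a patient without a target lesion, one of the two routes to the responder label is closed at registration, however much the tumour shrinks. A real partial response would then sit in the non-responder group, and any texture value read for that patient would be set against the wrong label. The sensitivity, specificity and predictive values planned in Section 14.2 rest on these labels. ORR would be lowered in the same direction. Section 14.2 allows only 4 patients beyond the 80 evaluable it needs (84 recruited).

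**Working it through.** **Inputs.** Response rate 35%, 80 evaluable patients and 84 recruited, all from Section 14.2. The number of patients whose only CT-measurable disease is in the skin (k) and the share of their responses that are CR (c) are not in the documents, so both are varied as assumptions.

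**The plan's own figure.** Expected responders are 0.35 × 80 = 28, and non-responders 80 − 28 = 52. Section 14.2 gives 20-25 and 55-60, which would correspond to 20/80 = 25% up to 25/80 = 31.25%. The stated split does not follow from the stated rate. That is a separate matter and nothing here depends on it; 28 is used as the reference.

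**Following one patient through the rules.** Take, as an illustration, a 20 mm skin metastasis visible on contrast CT with no other measurable disease.

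1. 5.1.2: 20 mm is at least 10 mm on CT, so the criterion is met.
2. 10.2.3 and 10.2.4: the lesion is skin, so it is non-target. The patient has no target lesion.
3. 10.1.2: after one cycle and a re-evaluation, the patient is evaluable for response.
4. The lesion shrinks to 10 mm, a decrease of (20 − 10)/20 = 50%. As a target lesion this would exceed the 30% needed for PR. As non-target disease it falls in the Non-CR/non-PD row of Table 1; under iRECIST, iPR is likewise unavailable.
5. If the lesion disappears, along with any other non-target disease, and tumour markers are normal, Table 1 gives CR and the patient is a responder.

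The rule therefore loses partial responses and keeps complete ones.

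**Size.** Assume the 35% rate also applies to these patients. Then

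expected responders lost = k × 0.35 × (1 − c).

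| k (assumed) | c = 0 | c = 0.5 | c = 1 | Responders of 80 at c = 0 |
|---|---|---|---|---|
| 1 | 0.35 | 0.17 | 0 | 27.65 (34.6%) |
| 2 | 0.70 | 0.35 | 0 | 27.3 (34.1%) |
| 4 | 1.40 | 0.70 | 0 | 26.6 (33.3%) |
| 8 | 2.80 | 1.40 | 0 | 25.2 (31.5%) |

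The bound that does not depend on k is the loss per patient: at most 1 × 0.35 × (1 − 0) = 0.35.

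**The case against.** Four points can be made on the other side.

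*CR is open to these patients.* A reader might infer that they enter the primary comparison as non-responders by rule. The documents do not support that. CR is available under Table 1 and under the Table 3 note, and CR counts towards ORR. Nor does any section say on which side Non-CR/non-PD falls; treating it as non-response is an inference from ORR being PR plus CR. This stands, and the point is limited accordingly.

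*Texture.* A reader might also infer that such a patient offers no lesion for texture analysis. Section 13.1 and Appendix VI do not restrict texture reading to target lesions, so this has no source. If texture were in fact read only on target lesions, the patient would drop out of the texture comparison and could not be mislabelled there; the harm would be a lost place among the 84. If it is read on the skin lesion, the label problem applies.

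*The group is narrow.* The patient needs a skin lesion of at least 10 mm on contrast CT and no other CT-measurable lesion or node. Scheduled CT covers chest, abdomen and pelvis, with other sites only when clinically indicated, and disease measurable by calipers alone does not satisfy 5.1.2. This stands, and it suggests that k is small.

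*The effect is within chance variation.* The standard deviation of the responder count is √(80 × 0.35 × 0.65) = √18.2 = 4.3, above even the 2.8 at k = 8 with no CRs, and the plan calls the trial exploratory. This is fair as to ORR. But the error has one direction, is known in advance and is cheap to remove, which chance variation is not.

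**Conclusion.** The mismatch between 5.1.2 and Sections 10.2.3 and 10.2.4 is established from the text, and no section that I found closes it. An eligible, evaluable patient with only skin disease measurable on CT can be a responder through CR alone; partial shrinkage is recorded as Non-CR/non-PD and, on the natural reading, counts against response in the primary comparison and in ORR.

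The size is modest and uncertain: at most 0.35 expected responders lost per such patient, and none if all their responses are CR. This assumes the plan's 35% rate holds for them and that Non-CR/non-PD is treated as non-response. No overall percentage can be given, because the documents do not state how common these patients are. The point is worth acting on because it touches the label behind the primary objective and the remedy is small, not because a large bias has been shown.

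**What to change.** 1. Reword 5.1.2 and the synopsis to require at least one lesion, measurable by contrast-enhanced CT, that qualifies as a target lesion under 10.2.1 and 10.2.3. That rules out skin lesions as the sole qualifying site. Keep the allowance in 10.2.1 for irradiated lesions with documented progression; a blanket bar on irradiated lesions would contradict that section.
2. Add the item to the registration checklist. Section 7.1 already asks sites to confirm the Section 5.0 requirements.
3. For patients already registered with non-target disease only, state in Section 14 that they stay in the safety and OS analyses and are left out of the responder/non-responder texture comparison. Report their number, and give ORR with and without them. Define the group by disease at baseline, so that complete responders in it are left out as well and the exclusion does not depend on outcome.

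The cost is one sentence in two places, one checklist item and a short analysis rule. The downside is that a few patients with skin-only measurable disease are no longer eligible. Step 3 is useful even if accrual is complete.
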